
SAP Section	SAP Description	Change	Rationale
		
ITT analysis set in the disposition summary (Section 5.2).
	
3.1	<<null>>	
Two analytic approaches are planned using the ITT analysis set.
 
 • In the first approach, all data collected from patients will be included, regardless of continued adherence to their assigned study treatment. • In the second approach, data collected from patients during the treatment period will be included, up to the point at which patients discontinue from their assigned study treatment (on-treatment). For patients who completed treatment in this study, the treatment period will be defined from the first dose of study drug to the end of treatment (week 52) visit. For patients who prematurely discontinue treatment, the treatment period will be defined from the first dose of study drug to the last dose of study drug + 4 weeks. 
The analytic approach including all data collected from patients will be utilized as the primary approach to analysis for the primary endpoint (frequency of CAE). The on-treatment approach will be conducted as a sensitivity analysis for the primary endpoint. For the analysis of all other efficacy endpoints, the on-treatment approach will be utilized as the main approach to analysis. The analytic approach including all data collected from
	Clarification

SAP Section	SAP Description	Change	Rationale
		patients will additionally be conducted as sensitivity analyses for selected secondary endpoints.	
3.2	<<null>>	In this analysis, data collected from patients during the treatment period will be included, up to the point at which patients discontinue from their assigned study treatment. For patients who completed treatment in this study, the treatment period will be defined from the first dose of study drug to the end of treatment (week 52) visit. For patients who prematurely discontinue treatment, the treatment period will be defined from the first dose of study drug to the last dose of study drug + 4 weeks. This analysis will be used as the default approach for all safety endpoints.	Clarification
3.3	<<null>>	The PP analysis set will only be presented for the primary endpoint. In this analysis, data collected from patients during the treatment period will be included, up to the point at which patients discontinue from their assigned study treatment.	Clarification
3.4.1	Selected efficacy endpoints including CAEs (primary), pre-bronchodilator FEV ₁ , and blood eosinophils will be analyzed separately for patients aged 12 to <18 years and ≥18 years.	Selected efficacy endpoints including CAEs (primary), pre-bronchodilator FEV ₁ , AQLQ+12, ACQ-6 , and blood eosinophils will be analyzed separately for patients aged 12 to <18 years and ≥18 years. Age strata will be defined based on the age recorded in the clinical database.	Inclusion of 2 additional efficacy endpoints and clarification regarding definition of age strata
3.4.2	Selected efficacy endpoints including CAEs (primary), pre-bronchodilator FEV ₁ , and blood eosinophils will be analyzed separately for patients with baseline blood eosinophil levels 300/μL to <400/μL and ≥400/μL.	Selected efficacy endpoints including CAEs (primary), pre-bronchodilator FEV ₁ , AQLQ+12, ACQ-6 , and blood eosinophils will be analyzed separately for patients with baseline blood eosinophil levels 300/μL to <400/μL and ≥400/μL. Eosinophil strata will	Inclusion of 2 additional efficacy endpoints and clarification regarding definition of eosinophil strata

SAP Section	SAP Description	Change	Rationale
		be defined based on the baseline blood eosinophil level recorded in the clinical database.	
3.4.5	Selected efficacy endpoints including CAEs (primary), pre-bronchodilator FEV1, and blood eosinophils will also be examined for the following demographic subgroups:	Selected efficacy endpoints including CAEs (primary), pre-bronchodilator FEV1, AQLQ+12, ACQ-6 , and blood eosinophils will also be examined for the following demographic subgroups:	Inclusion of 2 additional efficacy endpoints. In addition, Europe region split into Eastern and Western Europe and region for Middle East/Africa added.
4.5, 6.2.2, 6.2.3, 6.2.6, 6.3, 6.3.9.2	For patients who completed treatment in this study, the treatment period will be defined from the day of randomization to the end of treatment (week 52) visit. For patients who prematurely discontinue treatment, the treatment period will be defined from the day of randomization to the last dose of study drug + 4 weeks.	For patients who completed treatment in this study, the treatment period will be defined from the first dose of study drug to the end of treatment (week 52) visit. For patients who prematurely discontinue treatment, the treatment period will be defined from the first dose of study drug to the last dose of study drug + 4 weeks.	Reference start date changed from day of randomization to day of first dose of study drug administration
5.2	<<null>> <<null>>	Patients will be categorized as completed the study if they either complete the study visits up to and including follow-up (Week 64, for patients not participating in the LTE study) or up to and including end of treatment (Week 52, for patients participating in the LTE study). KM plots will be provided for time to discontinuation from treatment to identify if there is a differential dropout pattern between the treatment groups.	Clarification, based on inclusion of the long term extension study New analysis added
5.3	<<null>>	Baseline demographics and patient characteristics will also be summarized separately for patients who discontinue from treatment and patients who complete treatment to investigate whether patients with and without missing values may have different characteristics at baseline.	New analysis added

SAP Section	SAP Description	Change	Rationale
6.2.2, 6.3.3.2	<<null>>	Age and blood eosinophil categories will be based on data recorded in the clinical database.	Clarification
6.2.3	<<null>>	The primary analysis with control variables for age and blood eosinophil categories based on data recorded in the IRT (as randomized). This analysis will only be performed if the number of discrepancies between data recorded in the IRT and the clinical database are sufficiently large (eg, 5% of total population).	New analysis added
6.2.3	On-treatment analysis: analysis of the primary endpoint including all exacerbations observed until treatment completion or until withdrawal from treatment, excluding any exacerbations observed after withdrawing from treatment. Per-protocol analysis: on-treatment analysis of the primary endpoint based on the per-protocol analysis set.	On-treatment : analysis of the primary endpoint including exacerbations during the treatment period (ie, observed until treatment completion or until withdrawal from treatment, excluding any exacerbations observed after withdrawing from treatment). Per-protocol : on-treatment analysis of the primary endpoint including exacerbations during the treatment period (ie, observed until treatment completion or until withdrawal from treatment, excluding any exacerbations observed after withdrawing from treatment) , based on the PP analysis set.	Clarification
6.2.5	An interaction p-value will be derived from a separate NB model including terms for treatment, subgroup, and treatment by subgroup interaction.	An interaction p-value will be derived from a separate NB model including additional terms for subgroup and treatment by subgroup interaction.	Clarification
6.3.3.2	<<null>>	The proportion of patients achieving an increase of >100 mL in FEV₁ from baseline to each scheduled visit will be summarized. A	New analysis added

SAP Section	SAP Description	Change	Rationale
		stratified (based on randomization strata) Cochran-Mantel-Haenszel (CMH) test will be used to analyze the proportion of patients achieving an increase of ≥ 100 mL in FEV₁ from baseline to Week 52.	
6.3.4.2	<<null>>	AQLO +12 at Week 52 will additionally be examined for the selected subgroups defined in Section 3.4. The analysis of subgroups will use a MMRM model similar to the one described above. Subgroups will be presented graphically using forest plots.	New analysis added
6.3.5.2	<<null>>	ACQ-6 at Week 52 will additionally be examined for the selected subgroups defined in Section 3.4. The analysis of subgroups will use a MMRM model similar to the one described above. Subgroups will be presented graphically using forest plots.	New analysis added
6.3.6.2	A stratified (based on randomization strata) CMH test will be used to analyze the proportion of patients achieving a reduction of ≥ 4 in the SGRQ score from baseline to Week 52.	A stratified (based on randomization strata) CMH test will be used to analyze the proportion of patients achieving a reduction of ≥ 4 in the SGRQ score from baseline to Week 32 .	Updated the timepoint for SGRQ responder analysis to be aligned with protocol.
7.3.1.6	<<null>>	Opportunistic Infections	New section added
7.5	Table 6	Table 6	PCS (potentially clinically significant) criteria for CPK changed to Grades 3-4
8.2.2			Clarification

SAP Section	SAP Description	Change	Rationale
		[REDACTED]	

APPENDIX A. IMPUTATION AND ANALYSIS STEPS FOR ANALYSIS OF THE FREQUENCY OF ASTHMA EXACERBATION

The following represents an outline of the planned methodology for the multiple imputation procedure for the primary analysis of the CAE variable. Minor deviations from this outline can be addressed in the discussion of the results in the CSR. In the situation that more significant updates are warranted, changes will be addressed in a SAP amendment to be finalized prior to database lock.

Step 1: Seed generation.

The seed generation utilized the code below, resulting in a seed (40880) that will be used in the analysis after unblinding.

```
data derived.seed;
  seed = int(time());
  put seed=;
  call symput('seed', left(seed));
run;
```

Step 2: Classify patients with missing data.

Patients in this study will be partitioned into the following 3 categories:

1. ET0; patients who completed all 52 weeks of treatment
2. ET1; patients who withdrew early from treatment but remained in the study contributing post-treatment follow-up data through Week 52
3. ET2; patients who withdrew early from treatment but elected not to remain in the study through Week 52

Step 3: Imputation of missing data.

Using the dataset of ET1 patients for each treatment group, fit a negative binomial regression model to the period of time after treatment withdrawal and estimate the mean number of exacerbations and dispersion parameter k . Let λ denote the estimated rate parameter for one month of duration. For each patient with missing data, derive the duration of missing exposure (T_M) for that patient calculated in months.

Let λ_M denote the unknown rate of exacerbations during the missing exposure period. The exacerbation rate λ_M will be simulated using a Gamma distribution with parameters $\alpha=1/k$ and $\beta=\lambda*k$. Then, the number of events during the missing exposure period will be imputed using a negative binomial distribution with mean λ_M*T_M and dispersion k . For each patient in ET2, sum the observed number of exacerbations during the treatment period with the simulated number during the missing exposure period to obtain the imputed number of exacerbations. This process will be repeated 10 times.

After each iteration, the output dataset of imputed values for ET2 from Step 3 will be appended to the existing data from ET0 and ET1 (from Step 2) to generate 10 complete datasets.

Step 4: Re-run the primary analysis model.

The negative binomial model will be fitted to the complete set of data for each of the 10 datasets using the same covariates that were used for the primary analysis. The model will include

log(follow-up time) as an offset variable, either excluding/including the summed duration of exacerbations, depending on the analysis. For patients with imputed number of exacerbations, complete follow up of 1 year is assumed. The summed duration of exacerbations will be calculated as summed duration of any exacerbations observed prior to treatment withdrawal + 8 days for each additional (imputed) exacerbation. The assumption of 8 days for the duration of exacerbations is consistent with the minimal duration of exacerbation as derived previously in the BREATH IV program.

Step 5: Multiple imputation and associated combining rules applied to propagate imputation uncertainty (Little and Rubin 2002).

The output datasets from Step 4 will contain inferential statistics for each imputation iteration. The SAS[®] procedure PROC MIANALYZE will be used to generate an overall p-value and 95% CI for the treatment difference; results will be exponentiated back to their original scale.

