#### **4.4.1. Discontinuation of Study Treatment**

If premature discontinuation of study treatment occurs for any reason, the patient should continue attending remaining study visits while off study treatment. The patient should not be considered withdrawn from the study due to interruption or discontinuation of study treatment. For this study, it is very important to continue collecting data from all patients whether or not they complete treatment.

If premature discontinuation of study treatment occurs, the patient should return to the clinic as soon as possible for a study treatment discontinuation visit. All evaluations should be performed as an unscheduled visit and include all the assessments specified in the protocol for the early withdrawal visit (see Table 2). The investigator must determine the reason for and the date of discontinuation of study treatment and record this information in both the source documentation and the Study Drug Treatment Completion CRF. The patient's continued participation in the study must be discussed by the investigator and site staff with the patient; the investigator and site staff must also request the patient to continue attending study visits according to the study visit schedule with all assessments completed up to week 52 (visit 17). The CAE event status and safety assessments at week 52 (visit 17) are the priority assessments for patients that prematurely discontinue study treatment. At a minimum, the investigator should make every effort to obtain information regarding serious adverse events, CAE events, and survival status at week 52. A safety follow-up visit (visit 18) should be conducted 12 weeks after visit 17.

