3.1. Intent-to-Treat Analysis Set

The intent to treat (ITT) analysis set will include all randomized patients, with the exception of patients from Site [REDACTED] who will be excluded. In this population, treatment will be based on the treatment to which patients were randomized, regardless of which treatment they actually received.

Two analytic approaches are planned using the ITT analysis set.

- In the first approach, all data collected from patients will be included, regardless of continued adherence to their assigned study treatment.
- In the second approach, data collected from patients during the treatment period will be included, up to the point at which patients discontinue from their assigned study treatment (on-treatment). For patients who completed treatment in this study, the treatment period will be defined from the first dose of study drug to the end of treatment (week 52) visit. For patients who prematurely discontinue treatment, the treatment period will be defined from the first dose of study drug to the last dose of study drug + 4 weeks.

The analytic approach including all data collected from patients will be utilized as the primary approach to analysis for the primary endpoint (frequency of CAE). The on-treatment approach will be conducted as a sensitivity analysis for the primary endpoint. For the analysis of all other efficacy endpoints, the on-treatment approach will be utilized as the main approach to analysis. The analytic approach including all data collected from patients will additionally be conducted as sensitivity analyses for selected secondary endpoints.

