6.2.2. Primary Analysis

The primary analysis of frequency of CAEs will be analyzed using the general linear model (GLM) for data from the negative binomial distributions that is commonly referred to as the negative binomial (NB) regression model. The primary NB model will include the treatment group, randomization stratification factors (age and blood eosinophil categories, as defined in Section 2.4), and the number of exacerbations in the previous year as model factors and an offset variable. The offset variable will be calculated as the logarithm of follow-up duration minus the summed duration of exacerbations during the follow-up. Age and blood eosinophil categories will be based on data recorded in the clinical database.

The ratio of CAE rate between the treatment groups and its 95% confidence interval (CI) will be estimated from the NB model. Treatment effect will be evaluated using the likelihood based chi-square test. Clinical asthma exacerbations that occur between the first dose of study drug and 2 weeks after the end of treatment/early withdrawal visit will be counted towards the CAEs for analysis.

The primary analysis will incorporate data from all randomized patients. The analysis will include all exacerbations observed over 52 weeks, for patients who completed the 52 week treatment period and for patients who withdrew from treatment earlier than 52 weeks but from whom the sponsor was able to collect data post withdrawal. For early withdrawal patients that the sponsor will fail to retrieve data post withdrawal despite all attempts to contact the patient, a multiple imputation will be performed for the frequency of exacerbation post withdrawal. The multiple imputations will utilize the post withdrawal data observed for patients who withdrew early and for which the sponsor succeeded to retrieve the data. The methodology and algorithm used for imputations is described in [Appendix A](#).

The following sample Statistical Analysis Software (SAS®) code pertains to the primary efficacy analysis of CAEs.

```
proc genmod data=<<>>;
  class treatment strata1 strata2;
  model cae=treatment strata1 strata2 nexac /dist=negbin link=log offset=log_futime;
  estimate "CAE rate ratio" treatment 1 -1;
  lsmeans treatment /diff exp cl;
  ods output lsmeans=<<>>;
  ods output lsmeandiffs=<<>>;
run;
```

A frequency distribution bar graph will be provided for the number of CAEs by treatment group.

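### SAP Appendix A fits the off-drug CAE rate only to patients followed to Week 52 and makes no use of the observed off-drug follow-up of those who leave sooner

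*SAP*

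**What the plan says.** Step 2 of SAP Appendix A sorts patients into three groups: ET0 completed treatment, ET1 is "patients who withdrew early from treatment but remained in the study contributing post-treatment follow-up data through Week 52", and ET2 is "patients who withdrew early from treatment but elected not to remain in the study through Week 52". Anyone who stops drug and leaves before Week 52 is therefore ET2, however long they were observed off drug.

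Step 3 takes its rate and dispersion from ET1 alone: "Using the dataset of ET1 patients for each treatment group, fit a negative binomial regression model to the period of time after treatment withdrawal". For each ET2 patient it then instructs the programmer to "sum the observed number of exacerbations during the treatment period with the simulated number during the missing exposure period". For early discontinuers, SAP 3.1 has the treatment period "defined from the first dose of study drug to the last dose of study drug + 4 weeks". Step 4 assumes one year of follow-up for imputed patients. It subtracts the durations of CAEs seen before treatment withdrawal plus 8 days per imputed CAE.

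SAP 6.2.2 describes the source data more broadly: "The multiple imputations will utilize the post withdrawal data observed for patients who withdrew early and for which the sponsor succeeded to retrieve the data". Protocol 9.5.6.1 says the same in substance, and neither sets a Week 52 condition. SAP 6.2.2 also says that the analysis covers every CAE observed in the 52 weeks, including those of discontinuers from whom data were collected afterwards. SAP 3.1 assigns the approach that uses all collected data, regardless of adherence, to the primary endpoint.

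**The concern.** Protocol 4.4.1 asks that after stopping drug "the patient should continue attending remaining study visits while off study treatment", so some patients may be followed off drug for a time and then leave. Their observed off-drug person-time is the same kind of information that Step 3 needs, yet the ET1 definition shuts it out.

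Reaching Week 52 can depend on the outcome. If a CAE off drug prompts some patients to leave, those who stay are the ones with fewer CAEs, and a rate fitted to them is too low. That rate and dispersion drive every imputed count in the primary analysis.

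The second gap is in the ET2 patient's own total. Step 3 adds treatment-period CAEs to simulated CAEs and has no term for CAEs observed between the end of the treatment period and study exit. The start of the missing exposure T_M is not defined either. If it starts at study exit, the observed off-drug interval counts as event-free follow-up. If it starts at treatment stop, observed data are replaced by simulated draws.

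**Working it through.** **Inputs from the documents** (SAP 2.3, SAP 4.3, Protocol 9.1): placebo rate 2.9/yr; dispersion k = 1.2; 45% reduction, so 2.9 × 0.55 = 1.595/yr on reslizumab; two-sided alpha 0.05; 225 per arm.

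**The plan's own figure.** The plan gives no figure for the imputation, so its power statement is used to check the rate and dispersion. Var(log rate ratio) = (1/2.9 + 1/1.595 + 2 × 1.2)/225 = 3.372/225 = 0.01499, so SE = 0.1224. |ln 0.55|/SE = 0.598/0.1224 = 4.88, and 4.88 − 1.96 = 2.92, giving 99.8% power. This agrees with more than 99% in the protocol synopsis and with more than 90% in Protocol 9.1 and SAP 2.3.

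**Assumed, because the documents give no figures:** the probability p that an off-drug CAE prompts leaving, the length T of off-drug time to Week 52, the share of patients who discontinue, and the rate of leaving for other reasons.

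**Closed form for those who stay.** Let a patient's off-drug rate be gamma distributed with mean λ and dispersion k. The chance of staying for time T at individual rate Λ is exp(−pΛT). Weighting the gamma by this, and keeping only CAEs that did not prompt leaving, gives

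rate among stayers = λ(1 − p)/(1 + k·p·λ·T).

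With λ = 2.9, k = 1.2 and T = 0.5 yr:
- p = 0.05: 2.9 × 0.95/1.087 = 2.53
- p = 0.10: 2.9 × 0.90/1.174 = 2.22
- p = 0.20: 2.9 × 0.80/1.348 = 1.72

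**Simulation with negative binomial maximum-likelihood fits** (off-drug time 3 to 9 months, unrelated leaving at 0.3/yr, 60,000 patients per case):

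| True rate | p | ET1-only fit | Fit to all observed off-drug time |
|---|---|---|---|
| 2.9 | 0 | 2.90 | 2.90 |
| 2.9 | 0.05 | 2.54 (−12%) | 2.89 |
| 2.9 | 0.10 | 2.24 (−23%) | 2.91 |
| 2.9 | 0.20 | 1.70 (−41%) | 2.90 |
| 1.595 | 0.05 | 1.45 (−9%) | 1.61 |
| 1.595 | 0.10 | 1.32 (−17%) | 1.59 |
| 1.595 | 0.20 | 1.07 (−33%) | 1.58 |

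The recovery depends on the likelihood fit with log(observed off-drug time) as offset. With drug stopped between 15% and 85% of the year, crude events divided by person-time over all observed off-drug time gives 2.77, 2.65 and 2.48 at p = 0.05, 0.10 and 0.20. It is therefore not a substitute for the fit.

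**Effect on the rate ratio** (expected counts; 10% or 20% discontinue; p from 0.10 to 0.30). Take 20% discontinuing, half a year off drug on average, and reslizumab patients returning to 2.9/yr off drug. The true reslizumab mean is 0.8 × 1.595 + 0.2 × (0.5 × 1.595 + 0.5 × 2.9) = 1.726, and 1.726/2.9 = 0.595.
- Off-drug reslizumab rate equals placebo: the true ratio of 0.57 to 0.60 becomes 0.56 to 0.58 under Appendix A, whichever start of T_M is used. This favours reslizumab by about 0.01 to 0.03.
- The 45% reduction persists off drug: 0.550 becomes 0.551 to 0.554, slightly against reslizumab.
- With the fix, the first case gives 0.569 to 0.571 against a true 0.57 (10% discontinuing) and 0.588 to 0.592 against 0.595 (20%). A small shortfall remains because leavers, who tend to be the higher-rate patients, are still imputed at the arm average.

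**The case against.** A reader might infer that Appendix A flatly contradicts SAP 6.2.2 on which patients inform the imputation. The documents do not support that. SAP 6.2.2 speaks only of data retrieved or not retrieved, does not mention partial follow-up, and sends the reader to Appendix A for the algorithm. Requiring follow-up to Week 52 can be read as one way of defining retrieval, so on the source data Appendix A is narrower than 6.2.2 rather than opposed to it. That reading does not rescue the omission of ET2's observed off-drug CAEs, which conflicts with the all-observed-data statements in 3.1 and 6.2.2.

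The affected group may also be small. Protocol 4.4.1 and 4.4.2 ask sites to obtain CAE status at Week 52 even for patients who miss visits or are lost to follow-up. CAEs up to four weeks after the last dose are kept. Only patients who stop drug, are followed beyond that point and then leave unretrieved are affected. This stands, and the documents give no count of them.

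The tipping point analysis in Appendix B is not an answer, because it reuses Steps 1 to 3 and so starts from the same ET1-only rate.

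**Conclusion.** Appendix A should be corrected, but the point is about consistency and use of data more than a threat to the trial's conclusion. Two things follow from the text alone: ET2's observed off-drug time does not inform the imputation model, and, read literally, ET2's observed CAEs after the treatment period are not counted.

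The low bias in the fitted rate is conditional. It appears only if an off-drug CAE makes leaving more likely. Under assumed probabilities of 5% to 20% per CAE, it runs from about 12% to 41% at 2.9/yr and from 9% to 33% at 1.595/yr. If leaving is unrelated to CAEs, the ET1-only rate is unbiased and the loss is one of information.

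A reader might go further and infer that the primary result is biased towards reslizumab. The documents do not support that. The shift in the rate ratio is about 0.01 to 0.03 in reslizumab's favour if its off-drug patients return to the placebo rate, and 0.004 or less against it if the effect persists. Neither the off-drug rates nor the discontinuation share is given, and planned power is above 99%.

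**What to change.** Three edits to Appendix A, made by SAP amendment before database lock, a route the appendix already provides for:

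1. In Step 3, fit the off-drug negative binomial model by arm to all observed follow-up after treatment withdrawal, from ET1 and from ET2 up to the date of leaving, with log(observed off-drug time) as offset. Keep ET2 only as the label for patients who need imputation.
2. In Steps 3 and 4, include ET2's observed off-drug CAEs and their durations in the patient's own total.
3. Define T_M as starting on the last date at which CAE status was ascertained.

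The cost is a few sentences and some reprogramming. No new data are needed.

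### The primary imputation applies the negative binomial dispersion twice, holds its parameters fixed across imputations, and can leave the log offset undefined

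*SAP*

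**What the plan says.** SAP Appendix A sorts patients into completers (ET0), discontinuers followed to Week 52 (ET1) and discontinuers who are not (ET2).

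Step 3 opens with the instruction "Using the dataset of ET1 patients for each treatment group, fit a negative binomial regression model", applied to the time after treatment withdrawal. It yields a monthly rate λ and a dispersion k. A quantity λ_M is said to "denote the unknown rate of exacerbations during the missing exposure period", and it "will be simulated using a Gamma distribution with parameters" α = 1/k and β = λk. Then "the number of events during the missing exposure period will be imputed using a negative binomial distribution with mean" λ_M × T_M and dispersion k, where T_M is the patient's missing time. This is done 10 times, and no step redraws λ or k. Step 5 nevertheless describes the combining rules as propagating imputation uncertainty.

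In Step 4, "For patients with imputed number of exacerbations, complete follow up of 1 year is assumed". Exacerbation days are the observed days plus "8 days for each additional (imputed) exacerbation". The primary offset (SAP 6.2.2) is the log of follow-up minus exacerbation days. The first sensitivity analysis in SAP 6.2.3 does not subtract those days.

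Appendix B reuses these steps and multiplies the imputed reslizumab counts by a scale factor.

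**The concern.** A gamma-distributed rate followed by a Poisson count is already a negative binomial. A second negative binomial draw makes the imputed counts too variable. Holding λ and k at estimates from what may be a small ET1 group does the reverse: the ten datasets differ too little, and the combined standard error misses the uncertainty in λ and k. These steps produce the primary rate ratio, confidence interval and p-value.

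Step 4 adds a separate difficulty. The inflated upper tail meets a subtraction with no floor, so the records with the most imputed events may have no usable offset. The programmer would then have to make an unplanned choice.

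**Working it through.** **1. The plan's own figure.** Inputs from SAP 2.3: placebo rate 2.9 per year, k = 1.2, 45% reduction (1.595 per year), 225 per arm, alpha 0.05 (two-sided, SAP 4.3).

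SE of the log rate ratio = √[(1/2.9 + 1/1.595 + 2 × 1.2)/225] = 0.1224. Power = Φ(0.598/0.1224 − 1.96) = 99.8%, which agrees with the protocol synopsis (>99%). So k = 1.2 is the usual dispersion, with variance m + k·m².

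**2. Dispersion applied twice.** Let m = λ × T_M. The gamma mean is (1/k)(λk) = λ if β is a scale, which the SAP does not state. Then

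Var(N) = E[λ_M T_M + k(λ_M T_M)²] + Var(λ_M T_M) = m + k(1+k)m² + k·m² = m + k(2+k)m².

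At k = 1.2, k(2+k) = 3.84, which is 3.2 times the intended value. At the placebo rate:

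| Missing months | m | Variance intended | Variance as written |
|---|---|---|---|
| 6 | 1.45 | 4.0 | 9.5 |
| 12 | 2.90 | 13.0 | 35.2 |

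**3. Joint effect of the two errors.** The documents give no dropout or retrieval rate, so every dropout pattern here is an assumption. Steps 2–5 were simulated with 225 per arm, k = 1.2, 10 imputations and uniform withdrawal times.

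Type I error (%), primary offset, covariates in the model, 1500 trials per pattern, Monte Carlo SE 0.5–0.7 points:

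| ET1/ET2 per arm | As written | Dispersion corrected only | Both corrected |
|---|---|---|---|
| 11/11 | 5.5 | 6.4 | 5.6 |
| 17/17 | 4.2 | 5.0 | 4.7 |
| 11/23 | 5.2 | 6.0 | 4.9 |
| 14/42 | 5.1 | 7.3 | 5.1 |

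Coverage as written was 93.9–95.3%, and bias in the rate ratio was at most 0.5%. Runs without covariates (2000 and 3000 trials) gave 5.5% and 6.2% at 14/42, and 5.9% and 6.0% at 9/36.

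Type I error (%), full-follow-up offset, no covariates, 1200 trials per pattern, Monte Carlo SE 0.6–0.8 points:

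| Discontinue / ET2 share | As written | Both corrected |
|---|---|---|
| 10% / half | 5.0 | 4.9 |
| 20% / half | 4.9 | 5.2 |
| 20% / 80% | 7.4 | 5.2 |
| 30% / 80% | 7.4 | 5.7 |

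Correcting the dispersion alone gave 8.7% and 10.4% in the last two rows. A further 2800-trial run at 9/36 gave 7.4% as written. Two 500-trial runs with mostly ET2 patients gave 6.2% and 8.0%.

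**4. Undefined offset.** 45 × 8 = 360 days, but 46 × 8 = 368 > 365. At k = 1.2 and the placebo rate, P(46 or more imputed events) is 0.10% at 9 and 0.19% at 11 missing months. With a single-dispersion draw it is about 0.0002% or less.

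At least one undefined record among the 10 datasets occurred in 8–25% of trials in the first set of simulations and 20–48% in the second. The figure depends on the dropout pattern and on how extreme estimates of k are handled. In the second set it was 1–7% with a single-dispersion draw and fixed parameters, but 7–32% once parameters were redrawn without a count limit. So a limit is needed as well.

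**5. How many events can fit.** With 8-day events and the 7-day merging rule (SAP 6.2.1), n distinct events need 8 + 15(n − 1) days. In a year 24 fit (353 days); a 25th would end on day 368. At 11 missing months (335 days) 22 fit (323 days). Yet 24 or more are imputed in 1.3% of such records as written, against about 0.1% with a single-dispersion draw.

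**6. Appendix B.** If days follow the scaled count, scale 4 turns 12 imputed events into 48, or 384 days. With T_M uniform over 1–11 months and off-treatment rates equal to placebo, that affects about 2% of imputed reslizumab records as written and 0.7% with single dispersion.

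**The case against.** The strongest reply is that no harm to the primary analysis has been shown. With the primary offset, type I error as written stays near 5%. In the 14/42 pattern the mean reported SE matches the empirical SD (0.145 against 0.144), while the corrected method is somewhat too wide (0.153 against 0.142) and loses power. Protocol 4.4.1 asks sites to obtain CAE status at week 52 for patients who stop treatment, so patterns dominated by ET2 are pessimistic. The undefined offset touches about 0.05–0.2% of imputed records and does not arise with the full-follow-up offset. The on-treatment sensitivity analysis does not use this imputation. The appendix calls itself an outline and lets minor deviations be explained in the CSR.

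Most of this stands as a statement about size. It does not make the method sound. The agreement comes from two errors cancelling at a retrieval split that nobody has stated, and it fails with the other planned offset when few discontinuers are retrieved. The same outline clause sends more significant updates to a SAP amendment before database lock.

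A reader might infer that λ_M is drawn once per arm. Step 3 derives T_M and sums events patient by patient, so one draw per patient is the natural reading.

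A reader might also infer that observed off-treatment CAEs of ET2 patients are discarded, because Step 3 says to "sum the observed number of exacerbations during the treatment period with the simulated number during the missing exposure period" and Step 4 uses the "summed duration of any exacerbations observed prior to treatment withdrawal". Losing events requires both that the treatment period ends 4 weeks after the last dose and that T_M starts at study exit. SAP 3.1 and 6.2.2 call for all collected data. This is a wording gap, not a demonstrated loss.

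**Conclusion.** The concern holds and should be fixed. Step 3 is wrong as written on two counts, and Step 4 has no rule for a case that its own arithmetic permits.

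The effect on inference is modest and conditional: type I error of about 4–6% with the primary offset, and about 6–8% with the full-follow-up offset when most discontinuers are ET2. Neither claim that might be drawn from this is supported. The documents do not show that the primary p-value is invalid, and they do not guarantee that the two errors cancel. Correcting only the double dispersion generally makes the understated uncertainty worse.

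All trial-level figures rest on assumed dropout, retrieval and off-treatment rates, and on withdrawal unrelated to the patient's exacerbation rate. The variance formula and the 46-event threshold follow from the SAP text alone. The stated sample size and power are not affected.

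**What to change.** Amend SAP Appendix A Steps 3–4 before database lock, making these changes together:

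- (a) Draw λ_M per patient and the count from Poisson(λ_M × T_M), or draw the count once from a negative binomial with mean λ × T_M and dispersion k.
- (b) In each imputation, draw λ and k from their estimated sampling distribution, with limits stated in advance on the drawn k and on the SD of the draws. The version simulated used k from 0.05 to 5 and an SD of at most 1 on the log scale. Limits matter because arm-level ET1 estimates of k fell below about 0.05 or above 4 in 11–22% of simulated fits. Pooling k across arms is an option for stability, not a requirement.
- (c) Limit the imputed count to what fits in the missing time, given 8-day events and the 7-day merging rule, so that the offset stays defined. Apply the same limit after scaling in Appendix B.

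As a clarification of wording only, start T_M at the last date with CAE information, and keep all observed CAEs and exacerbation days up to that date.

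The cost is a short amendment, modest programming and a somewhat wider interval when ET2 patients are many. With pooled k, power was 88.6% instead of 91.7% at 14/42 and 95.1% instead of 96.1% at 11/23. Arm-specific k gave 86.3% at 14/42. The simulated version limited imputed days rather than counts, so (c) should be checked when programmed. At k = 1.2 and the placebo rate, a limit of 8 + 15(n − 1) days lowers the imputed mean by about 0.2% at 11 missing months and 0.8% at 3.
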